In December 2017, a trial compared a chewed sublingual form of ticagrelor to standard pill form in patients with STEMI. It also showed more rapid absorption and platelet inhibition within hours of drug administration. To our knowledge, our study will be the first to compare platelet reactivity in non ST segment elevation acute coronary syndrome (NSTE-ACS) and patients with stable CAD undergoing PCI who received chewed ticagrelor.

Specific Aims:

To compare the effect of ticagrelor chewed pills with the effect of equal dose of integral pills in decreasing platelet reactivity and adverse event rates in all patients being treated for NSTE-ACS and stable coronary artery disease, undergoing percutaneous coronary intervention.

Primary objective:

Determine platelet inhibition at baseline, and early at 1 hour and 4 hours after loading dose.

Secondary objective:

Assess major adverse cardiac and cerebrovascular event (MACCE) rate at 30 days and 1 year.

1. Death;
2. Repeat myocardial infarction;
3. Need for urgent revascularization;
4. Cerebrovascular accident;
5. Rate of stent thrombosis and in-stent stenosis at 30 days and 1 year;
6. Bleeding: Defined as major, minor, or minimal bleeding based on TIMI criteria.

Hypothesis:

Chewed ticagrelor pill is superior to integral pill in decreasing platelet reactivity.

Primary Outcome Measures:

Residual platelet reactivity by Platelet Reactivity Units (PRU) VerifyNow 1 hour and 4 hours after ticagrelor loading dose (LD) and percent of patients with a high residual platelet reactivity (PRU > 208) 1 hour and 4 hours after ticagrelor LD.

Secondary Outcome Measures:

1. Bleeding events: Major, minor, minimal bleeding (TIMI criteria) events.
2. Occurrence of dyspnea and/or symptomatic bradycardia.
3. Major adverse cardiac and cerebrovascular event (MACCE) rate: Death, Myocardial infarction, Stent Thrombosis, Urgent revascularization, Cerebrovascular accident at 30 days and 1 year.

STUDY DESIGN

This will be an interventional study to evaluate the superiority of chewed ticagrelor in comparison to integral pill form. Superiority will be defined as a reduction of platelet reactivity in both groups undergoing PCI.

Study population will include 132 patients. They will be stratified into 2 groups: Patients with NSTEMI-ACS and patients with stable coronary artery disease (CAD) undergoing coronary angiography for non-urgent reasons.

Inclusion criteria:

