- 4. Patients presenting with NSTEMI-ACS or stable CAD undergoing coronary angiography for urgent or non-urgent reasons.

Exclusion criteria:

1. Age <18 years or Age >90 years;
2. Known coagulopathy, bleeding diathesis, or active bleeding;
3. Known chronic therapy with clopidogrel, prasugrel, or ticagrelor;
4. Known history of intracranial bleed or intracranial neoplasm;
5. Suspected aortic dissection;
6. Severe hemodynamic instability, cardiogenic shock;
7. Life expectancy <1 year;
8. Known severe liver or renal disease (CrCl < 30, or dialysis dependent);
9. Taking drugs known to interfere with CYP3A4 metabolism (Azoles, Clarithromycin, Ritonavir, Saquinavir, Nelfinavir, Indinavir, Atazanavir);
10. Any use of GP IIb-IIIa inhibitors 48-hours before the procedure or any use during the procedure;
11. Any use of Cangrelor during or after the procedure;
12. Hemoglobin <10 g/dL, PLT <80x10⁹/L;
13. Pregnant or lactating females;

14. Known allergy to study medication;
15. Fibrinolytic use within past 48 hours;
16. Inability to give consent;
17. Known sick sinus syndrome (SSS) or high degree AV block without pacemaker protection.

Written informed consent:

Patients presenting for both urgent and elective left heart catheterization will be consented by the personnel delegated by the investigator before any study-related activity.

Randomization:

Patients will be randomized prior to PCI. Patients from each strata (NSTE—ACS, and patients with stable CAD) will be randomized in a 1:1 fashion to receive a loading dose of 180mg ticagrelor in integral pill form (swallowed) or chewed form.

Study procedures:

Patients admitted to the inpatient cardiology service with NSTE-ACS meeting eligibility criteria are often treated medically before reaching the catheterization suite for coronary angiography and possible percutaneous coronary intervention. These patients often receive the loading dose of 180mg ticagrelor on the medical floor. In order to enroll these patients, the baseline PRU level blood draw, can be obtained on the floor before that loading dose is administered. The subsequent 1-hour and 4-hour blood draws can be obtained on the medical floor or in catheterization suite.

[figure not shown]

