Data will be collected by the personnel delegated by the PI. Preliminary data will be analyzed after enrollment of 65 patients.

Timeline /Schedule of events

	Visit 1 Baseline	Visit 2 Procedure	Visit 3 Post Procedure	Visit 4 Discharge	Visit 5 30 day follow up- (+/- 14 d) EMR-Chart review	Visit 6 1 yr follow up- (+/- 14 d) EMR-Chart review
Inclusion/ Exclusion	X					
Informed Consent Obtained	X					
Demographics, Medical History, Con Meds	X					
Angiography /PCI Procedure		X				
Blood draw for PRU	X baseline, 1-hour and 4- hour levels can be collected before coronary angiograp hy for patients admitted to hospital floor	X	1 h after PCI 4h after PCI			

	before procedure					
MAACE Event documentation				X	X	X

Statistical Analysis

Patient characteristics will be presented as proportions for categorical variables and mean \pm standard deviation (SD) and or Median [lower quartile (01) - upper quartile (03)] for continuous variables. Comparison of categorical variables for patients who will receive integral pill form of ticagrelor and the other the chewed form will be performed using the chi-square and Fisher's exact test while the two sample t test will be done to assess differences in continuous patient characteristics. Visual displays of event free Survival and cumulative incidence curves will be generated by the Kaplan-Meier approach and event free survival among groups compared using the log rank test. In addition to time point analysis, an alternating logistic regression (ALR) will be fitted to evaluate P2Y12 reaction units (PRU) levels at baseline (before LD), 1 hour, and 4 hours. Further analysis will entail fitting both univariate and multivariate Cox proportional-hazards models to examine the association between baseline characteristics and each of outcomes: In-stent thrombosis and restenosis, MACCE, and the need for repeat revascularization within 1-year separately. All analyses will be done using SAS Version 9.4 (SAS Institute, Cary, NC) and tests performed at a 5% level of significance.

Monitoring Plan

The goal of monitoring in this study is primarily to make sure that the primary data are collected and recorded properly and consenting process was done.

The Principal Investigator will be responsible for monitoring the safety environment of the participants, and will ensure that

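### The log-rank test of event-free survival should name the randomised arms and be stratified by NSTE-ACS / stable CAD; as written it is valid by arm but slightly conservative

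*Combined protocol and SAP*

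**What the plan says.** The Specific Aims section sets chewed against integral pills "in decreasing platelet reactivity and adverse event rates in all patients being treated for NSTE-ACS and stable coronary artery disease". The event part is a secondary objective: "Assess major adverse cardiac and cerebrovascular event (MACCE) rate at 30 days and 1 year".

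Under Randomization, allocation is made separately by disease group: "Patients from each strata (NSTE—ACS, and patients with stable CAD) will be randomized in a 1:1 fashion".

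For time-to-event outcomes, the Statistical Analysis section describes Kaplan-Meier curves, with "event free survival among groups compared using the log rank test". It does not define the groups and names no stratification factor. The sentence before it does name a contrast: "Comparison of categorical variables for patients who will receive integral pill form of ticagrelor and the other the chewed form", by chi-square and Fisher's exact test. The Cox models that follow relate baseline characteristics to stent thrombosis and restenosis, MACCE and repeat revascularization. Neither treatment arm nor disease group is listed as a term.

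**The concern.** There are two gaps, of different weight.

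- **The contrast is not named.** No time-to-event analysis in the plan mentions the pill form, although a comparison of event rates by pill form is part of the stated aim. A reader has to infer the contrast from context.
- **The strata are used to randomise but not to analyse.** The Statistical Analysis section never mentions them. If the two disease groups differ in event risk, balanced allocation within strata makes the arms more alike than the ordinary log-rank variance assumes. That variance is then somewhat too large, so the test rejects too rarely under the null and loses some power. The arm effect is also not estimated within the strata in which patients were randomised.

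At stake is the clarity and, to a small degree, the efficiency of the secondary event comparison.

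**Working it through.** **Inputs from the documents.** 132 patients in total (Study Design); 1:1 allocation within each of two strata (Randomization); follow-up to 1 year; tests at the 5% level (Statistical Analysis).

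**No figure to reproduce.** The 132 comes with no effect size, SD, event rate, power or dropout, so it cannot be re-derived.

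**Assumptions, because the documents are silent.** A two-sided test; 66 patients per stratum, split exactly 33/33 by arm (88/44 across strata also tried); exponential event times censored at 1 year; the 1-year control-arm event rates shown in the table.

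**Statistics compared.** At each event time j, with d_j events and n_1j of n_j patients at risk in the chewed arm:

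- U = Σ(d_1j − d_j·n_1j/n_j) and V = Σ d_j·(n_1j/n_j)(1 − n_1j/n_j), with no ties
- Unstratified: reject if U²/V > 3.84, all patients pooled
- Stratified: compute U and V within NSTE-ACS (A) and stable CAD (C), and reject if (U_A + U_C)²/(V_A + V_C) > 3.84

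**Results, 20,000 simulated trials per row, unstratified v stratified:**

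| NSTE-ACS / stable CAD event rate | Type I error | Power at HR 0.5 | Power difference |
|---|---|---|---|
| 10% / 5% | 4.6% v 4.8% | 13.6% v 13.9% | 0.3 points |
| 15% / 5% | 4.8% v 5.1% | 17.3% v 18.2% | 0.9 points |
| 25% / 5% | 4.1% v 5.1% | 23.5% v 25.6% | 2.1 points |
| 30% / 10% | 4.2% v 4.9% | 31.1% v 33.0% | 1.9 points |
| 15% / 5%, split 88/44 | 4.6% v 4.9% | 19.8% v 20.3% | 0.5 points |

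The simulation standard error at a 5% rejection rate is √(0.05 × 0.95/20,000) = 0.15 points.

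At a hazard ratio of 0.4, a separate run of 8,000 trials per scenario gave 30% v 31% (20% / 5%) and 39% v 42% (30% / 5%), so 1 and 3 points. A further run with stable CAD at 5% and NSTE-ACS at 10% to 30% gave type I error of 3.9% to 4.9% unstratified and 4.4% to 5.0% stratified, with 0.6 to 3 points of power lost. The runs agree apart from simulation error. The smallest loss is 0.3 points in one and 0.6 in another, and neither matters in practice.

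**Scale of the comparison.** Expected events are 33 × [p_A + p_C + (1 − (1 − p_A)^HR) + (1 − (1 − p_C)^HR)]. At 15% / 5% and HR 0.5 this is 33 × (0.15 + 0.05 + 0.0780 + 0.0253) = 10.0. Across the equal-split rows of the table it runs from about 7 to 20. The Schoenfeld requirement for 80% power at HR 0.5 is 4(1.960 + 0.842)²/(ln 0.5)² = 4 × 7.85/0.480 = 65.4, so 66 events. The shortage of events limits this comparison far more than the choice of log-rank test.

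**The case against.** **The case for leaving the plan alone.** The sentence before the log-rank sentence names the two pill forms, and the aim compares them on adverse event rates, so a reasonable analyst would test by arm. That test does not inflate type I error. Stratifying adds at most about 3 points of power under rates that are themselves assumed, and it cannot rescue a comparison with so few events. The chi-square or Fisher comparison by pill form might also cover MACCE proportions.

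Most of this stands, and it is why the point is modest. The last part is uncertain: the chi-square sentence follows one on patient characteristics, does not name MACCE, and would ignore event timing and censoring. What remains is that the plan does not name its event contrast and does not use its randomisation strata.

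**A stronger reading that a reader might infer.** The Study Design section uses the word groups for the disease categories: "They will be stratified into 2 groups: Patients with NSTEMI-ACS and patients with stable coronary artery disease (CAD". It then says "Superiority will be defined as a reduction of platelet reactivity in both groups undergoing PCI", which also reads most naturally as the disease groups. The treatments are called arms in the intervention table. From this one might conclude that the log-rank test compares NSTE-ACS with stable CAD, and so says nothing about chewing. The documents do not establish that. Groups is never a defined term, the Randomization section calls the disease categories strata, and no objective or outcome asks for a comparison between them. The only contrast named in the Statistical Analysis section is integral versus chewed. The undefined word calls for clarification; it does not show that the wrong contrast will be tested. The two complaints also cannot be added together, because ignoring the strata matters only if the test is by arm.

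**Conclusion.** The point holds as a specification gap with a small statistical cost. The log-rank sentence does not name the arms, although chewed versus integral is the likely intention, and it ignores the strata used for randomisation. Read by arm, the test is valid and slightly conservative: type I error of about 3.9% to 4.9% against 4.4% to 5.0% stratified, and about 0.6 to 3 points less power at a hazard ratio of 0.4 to 0.5.

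These figures assume 66 patients per stratum, exact 1:1 balance within each, two-sided 5% tests, and 1-year event rates of 5% in stable CAD and 10% to 30% in NSTE-ACS. The cost shrinks as the two event rates come closer together. The point concerns a secondary outcome and leaves the primary PRU comparison untouched.

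**What to change.** Replace the log-rank sentence in the Statistical Analysis section with:

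> Event-free survival will be compared between the randomised arms (chewed versus integral) with a log-rank test stratified by NSTE-ACS / stable CAD, with a stratified hazard ratio and 95% CI; Kaplan-Meier curves will be shown by arm, overall and within each stratum.

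The cost is one sentence and a STRATA specification in the SAS code. Disease group is known for every patient at randomisation, so no patients, visits or data are added.

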Patients scheduled to undergo and elective (non-urgent) coronary angiography for stable CAD who meet eligibility criteria will have blood drawn for a baseline PRU level prior to administration of the study drug. After the procedure, two subsequent blood draws will be taken at precise times: 1 hour +/-60 minutes, and 4 hours +/- 90 minutes after loading dose administration. All other procedures are considered standard of care.

Arm	Intervention/Treatment
Arm One: Chewed ticagrelor pills (Loading dose 180mg)	Drug: Ticagrelor chewed pills. The loading dose will be administered as soon as possible by hospital floor nurse or Catheterization Lab staff after a baseline PRU level is drawn. Patients will be asked to

	chew and swallow followed by 25-50mL of water.
Arm Two: Integral pill form of ticagrelor (Loading dose 180mg)	Drug: Ticagrelor integral pills. The loading dose will be administered as soon as possible by hospital floor nurse or Catheterization Lab staff after a baseline PRU level is drawn. and before the end of the PCI . Patients will swallow the loading dose followed by 25-50mL of water.

Subject will have orders to continuing ticagrelor during admission status. After the 4th hour blood draw the primary outcome will be complete. Patients will be encouraged to remain on ticagrelor with an outpatient prescription to measure secondary outcomes.

Flow Chart

Patient's EMR will be reviewed at 30 days and at 1 year to document any primary or secondary outcome measures. Duration of the study is one year.

Data collection

Baseline Characteristics	Procedure Related information	Post-procedure Related Information
Gender		
Body mass index, kg/m ²	Consenting	PRU 1 hour
Current smoker	Randomization	PRU 4 hours
Hypertension	Baseline PRU test	Length of stay
Diabetes mellitus	Loading dose administration	Date of death
Dyslipidemia	Access (femoral, Radial)	Repeat MI
Prior coronary artery disease	Start catheterization	Stent thrombosis 30 days
Prior aspirin	Culprit vessel	CVA
Prior beta-blockers	Type of stent	Urgent Revascularization
Prior statins	Number of stents	
LVEF (%)	Fluoro time/dose	
Creatinine clearance, mL/min	Contrast volume	TIMI Minimal bleeding
Hemoglobin (gr/dl)	Narcotic use	TIMI Minor bleeding
Platelet count, 1,000/mm ³		TIMI Major bleeding
Low-density lipoprotein (mg/dl)		Access site complication (hematoma, pseudoaneurysm, need for surgical or percutaneous repair)
High-density lipoprotein (mg/dl)		

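### No stated comparison of PRU at 1 h or 4 h adjusts for baseline PRU or for the randomisation stratum, which gives up precision on the primary outcome

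*Combined protocol and SAP*

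**What the plan says.** Under Primary Outcome Measures, the primary outcome has two forms, each at 1 h and 4 h after the loading dose: the PRU value, and the "percent of patients with a high residual platelet reactivity (PRU > 208) 1 hour and 4 hours after ticagrelor LD".

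The design supplies two natural covariates for both forms:
- **Stratum.** Study Design states: "Study population will include 132 patients. They will be stratified into 2 groups", namely NSTE-ACS and stable CAD. The Randomization section allocates 1:1 within each.
- **Baseline PRU.** Under Study procedures, elective patients "will have blood drawn for a baseline PRU level prior to administration of the study drug". For floor patients the same section allows the baseline draw before the loading dose. The intervention table places the dose after the baseline draw in both arms.

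The Statistical Analysis section offers three things that could apply to PRU. Chi-square and Fisher's exact tests compare categorical variables between arms. For continuous variables, "the two sample t test will be done to assess differences in continuous patient characteristics". Then: "In addition to time point analysis, an alternating logistic regression (ALR) will be fitted to evaluate P2Y12 reaction units (PRU) levels at baseline", 1 hour and 4 hours. Time point analysis is not defined and no covariates are listed for the regression. The only models with covariates are the Cox models for clinical events.

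**The concern.** PRU before the dose may predict PRU after it, and acute and stable patients may differ in level. The trial collects the first and stratifies on the second, yet the Statistical Analysis section uses neither in comparing the arms at 1 h or 4 h. Listing baseline as one of the times in a repeated-measures model is not a stated adjustment for it.

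What is at stake is precision on the primary outcome in a trial of 132 patients: wider confidence intervals and lower power than the same data could give. If the strata differ in mean PRU and allocation is balanced within them, an unadjusted t test also rejects less often than its nominal 5%, because it counts the between-stratum spread as noise.

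**Working it through.** **Inputs from the documents.** 132 patients randomised 1:1, so 132 / 2 = 66 per arm; 5% significance level. The documents give no effect size, SD, correlation, event rate or power, so 132 cannot be reproduced and everything below is illustrative.

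**Assumptions.** Two-sided tests, normal PRU, no dropout, an effect that gives 80% power unadjusted, and no stratum effect beyond baseline unless stated.

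**Step 1: which stated analysis uses which covariate**

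| Analysis | Baseline PRU | Stratum |
|---|---|---|
| t test at each time (inferred reading) | not used | not used |
| Chi-square or Fisher at each time (inferred reading) | not used | not used |
| Alternating logistic regression | a time point, not a stated covariate | not mentioned |
| Cox models | clinical events only, not PRU | clinical events only, not PRU |

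**Step 2: unadjusted comparison.** The standard error of the difference is √(2/66) = 0.174 SD. A difference of 0.4913 SD has noncentrality 0.4913 / 0.1741 = 2.82 and, by the noncentral t on 130 degrees of freedom, power 0.800.

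**Step 3: ANCOVA with baseline and stratum.** With correlation r between baseline and follow-up PRU, the variance is multiplied by 1 − r² and the degrees of freedom fall to 128.

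| r | 1 − r² | CI width ratio √(1 − r²) | Noncentrality | Power |
|---|---|---|---|---|
| 0 | 1.00 | 1.00 | 2.82 | 0.800 |
| 0.2 | 0.96 | 0.98 | 2.88 | 0.816 |
| 0.3 | 0.91 | 0.95 | 2.96 | 0.836 |
| 0.45 | 0.80 | 0.89 | 3.16 | 0.880 |
| 0.6 | 0.64 | 0.80 | 3.53 | 0.938 |

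**Step 4: ignoring the stratum.** Assume two strata of equal size, balanced allocation within each, and means that differ by g within-stratum SDs. The t test then estimates a variance too large by the factor 1 + g²/4. Its true type I error is about P(|Z| > 1.96 √(1 + g²/4)): 5.0%, 4.3% and 2.8% for g = 0, 0.5 and 1. A simulation of 20,000 trials gave 5.1%, 4.4% and 2.8%.

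**Step 5: PRU > 208.** Assume 30% or 50% above the cut-off in the integral-pill arm, and simulate 6,000 trials per setting.
- The difference in percentages standardised from a logistic model with baseline and stratum has the same target as the unadjusted one (about −15 and −19 points). Its variance is 4% lower at r = 0.3 and 20–22% lower at r = 0.6.
- The odds ratio changes its target: from 0.42 and 0.45 unadjusted to 0.40 and 0.42 (r = 0.3) or 0.33 and 0.34 (r = 0.6). An adjusted odds ratio alone would therefore not match an endpoint stated as a percentage.
- Events may be few, and the documents give no rate for either time. At an assumed 5% in the integral-pill arm, the same shift gives Φ(−1.645 − 0.491) = 0.0163 in the chewed arm. Expected events are 66 × 0.05 = 3.3 and 66 × 0.0163 = 1.1, and the chance of none in the chewed arm is (1 − 0.0163)^66 = 34%. At an assumed 10% that chance is 8%. A logistic model with two further covariates may then fail to converge.

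**The case against.** **Unadjusted comparison of randomised arms is valid.** Adjustment is an efficiency choice, and at r of 0.2 or less the gain is under two points of power. This stands. A reader might infer from the missing covariates that the comparison is biased or the test invalid; the documents do not support that, because both arms are randomised within strata and the direction of any error in the t test is conservative. What remains is that the gain could be large, while the cost at r = 0 is negligible (power stays at 0.800).

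**The method for continuous PRU can be read from the plan.** A reader might infer that the plan has no analysis for half of its primary outcome, or that it would apply a logistic model to a continuous measure. The text is loose: the t test is tied to patient characteristics, and no response is stated for the regression. But the ordinary reading is a t test and a chi-square test at each time, plus the regression on PRU > 208, the only PRU cut-off in the documents. This is missing detail rather than a separate error, and on that reading the tests are still unadjusted.

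**The stratum may already be part of the success definition.** Study Design defines superiority as reduced platelet reactivity in two groups, which may mean the arms or the strata. If it means the strata, a pooled difference alone would not answer the criterion, and the 66-per-arm illustration would not apply. With an assumed 33 per arm in each stratum, power at 0.49 SD is about 50% unadjusted and 54–69% with r = 0.3–0.6. This stands as a reason to report within each stratum as well. It does not put the stratum into the Statistical Analysis section.

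**The stratum gain is not shown in the power table.** Correct: every gain in Step 3 comes from baseline PRU. The case for the stratum rests on Step 4 and its assumed differences.

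**Conclusion.** The concern holds as a should-fix point about precision. No comparison of PRU at 1 h or 4 h stated in the Statistical Analysis section adjusts for baseline PRU or for the stratum, even on the reading most favourable to the plan. That the text names no such adjustment is certain; the size of the loss is not.

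For continuous PRU at one time, the gain runs from nothing at r = 0 to 14 points of power (80% to 94%) and a 20% narrower confidence interval at r = 0.6. These figures rest on an assumed correlation, an assumed 80% starting power, normality and no dropout. The conservative t test rests on assumed stratum differences and on balanced allocation within strata; the documents give the 1:1 ratio within strata but no blocking. The logistic results apply to assumed rates of 30–50% above the cut-off and should not be carried over to a time at which few patients exceed it.

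**What to change.** Amend the Statistical Analysis section as follows.

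- **Continuous PRU.** Analyse by ANCOVA at 1 h and at 4 h, or by a mixed model with arm, time, arm-by-time and baseline-by-time, with baseline PRU and stratum as covariates. Report the adjusted arm difference with its 95% CI at each time. Show it within each stratum too, and state whether the groups in the superiority sentence of Study Design are the arms or the strata.
- **PRU > 208.** State that the alternating logistic regression takes PRU > 208 at 1 h and 4 h as its response, with baseline PRU and stratum as covariates. Where events allow, report the standardised difference in percentages with its 95% CI, naming the variance method.
- **Sparse events.** Pre-specify when a fallback applies and what it is, for example an unadjusted difference with an exact or score interval and Fisher's exact test.

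This also settles which method is meant for continuous PRU and what the regression models.

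The cost is analysis-plan text and some programming for the standardised difference and the fallback. There are no new data, visits or patients: both covariates are already available and use 2 of 130 degrees of freedom in the ANCOVA.

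### The Cox models of baseline characteristics have no limit on size although 132 patients can yield few events, and no hazard ratio for chewed versus integral is planned

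*Combined protocol and SAP*

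**What the plan says.** The Study Design section fixes the size of the trial: "Study population will include 132 patients". Under Randomization, patients in each of two strata (NSTE-ACS and stable CAD) are "randomized in a 1:1 fashion" to chewed or integral ticagrelor, so there are about 66 per arm.

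The Statistical Analysis section describes two sets of time-to-event analyses.

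- **Comparison among groups.** Kaplan-Meier curves and a log-rank test. The word for groups is not defined there; I read it as the two arms.
- **Further analysis.** This consists of "fitting both univariate and multivariate Cox proportional-hazards models to examine the association between baseline characteristics and each of outcomes". The outcomes are "In-stent thrombosis and restenosis, MACCE, and the need for repeat revascularization within 1-year separately".

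All of this is covered by one statement on error, "tests performed at a 5% level of significance", with no adjustment for the number of tests.

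The covariates are described only as baseline characteristics. The Data collection table has a column headed "Baseline Characteristics" with 16 entries, from gender and body mass index to LDL and HDL. The plan gives no list of covariates for the models, no selection rule, no cap on model size, no expected event rate and no planned number of events. The sentence on Cox models names neither the randomised arm nor the stratum.

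**The concern.** The information in a Cox model comes from events, not patients. A trial of 132 patients, sized for a platelet-reactivity endpoint and followed for one year by record review, can be expected to yield few clinical events. An open-ended multivariable model fitted to few events tends to give very large or very small hazard ratios, or does not converge, and chance associations look like predictors. With three outcomes and many characteristics each tested at 5%, some nominally significant predictors are likely even if none is real.

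MACCE is also a stated secondary outcome, for which the reader will want the difference between arms and its uncertainty. A log-rank test gives a p-value only. With few events that p-value will probably be uninformative, and the useful result is the confidence interval, which shows how large a benefit or harm remains possible. The plan specifies no such interval.

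**Working it through.** **Inputs from the documents:** 132 patients; 1:1 allocation; three outcomes modelled separately; 16 listed baseline characteristics; 5% per test (two-sided assumed).

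**Assumed, because the documents are silent:** one-year event rates of 2% to 15%, with 20% and 40% shown as high cases; a benchmark of 10 events per variable, with 5 as a lenient bound.

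**Reproducing the plan's figure.** The total of 132 is given without power, effect size, standard deviation, event rate or dropout, so it cannot be reproduced. No event count is planned for the Cox models.

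**Step 1. Events needed** = covariates x events per variable.

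- 16 covariates: 16 x 10 = 160, more than 132. At the lenient bound, 16 x 5 = 80, and 80/132 = 61% of patients.
- 2 covariates: 2 x 10 = 20, and 20/132 = 15.2%.

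**Step 2. Events expected** = 132 x rate.

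| Assumed rate | Events | Events per variable with 16 | Covariates supported at 10 per variable |
|---|---|---|---|
| 2% | 2.6 | 0.17 | 0 |
| 5% | 6.6 | 0.41 | 0 |
| 10% | 13.2 | 0.83 | 1 |
| 15% | 19.8 | 1.24 | 1 |
| 20% | 26.4 | 1.65 | 2 |
| 40% | 52.8 | 3.3 | 5 |

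The binomial chance of at least 20 events is 4% at a 10% rate and 52% at 15%. For stent outcomes 132 is an upper limit on the patients at risk, because the Study procedures section describes PCI as possible, not certain.

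**Step 3. How the fits behave.** The simulation used 132 patients, covariates with no true effect (with 16: nine binary, seven normal), a constant hazard and censoring at one year. A fit counted as not estimable if it had fewer than two events, a non-finite standard error or an absolute log hazard ratio above 8. An extreme hazard ratio is above 4 or below 1/4, among estimable fits. Ranges cover repeated simulations.

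| Covariates | Rate | Not estimable | Any extreme hazard ratio |
|---|---|---|---|
| 16 | 10-15% | 1-9% | 24-54% |
| 16 | 5% | about 52% | - |
| 16 | 2% | 91-95% | - |
| 5 | 5% | 21% | 28% |
| 2-3 | 10-15% | 0-2% | 1-8% |
| 2-3 | 5% | 10-19% | - |
| 3 | 2% | 58-66% | - |

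**Step 4. Number of tests.** Univariate screening of every listed characteristic is 16 x 3 = 48 tests, and 48 x 0.05 = 2.4 false positives are expected if there are no true associations. This expectation does not require independent tests. If the tests were independent, the chance of at least one false positive would be 1 - 0.95^48 = 91%. That is only a guide, because the outcomes overlap.

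**Step 5. Power for one predictor.** By Schoenfeld's formula, a balanced binary covariate with hazard ratio 2 needs 4(1.96 + 0.84)^2/(ln 2)^2, about 66 events, for 80% power. At event rates of 5%, 10% and 20%, power is 14%, 24% and 43%.

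**Step 6. What an interval for arm would show.** With events split about evenly, the standard error of the log hazard ratio is about 2/sqrt(events). For 13.2 events, exp(1.96 x 2/sqrt(13.2)) = 2.9; for 19.8 events it is 2.4. The 95% interval would run from the estimate divided by that factor to the estimate multiplied by it. A log-rank p-value alone would not show this width.

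**The case against.** Several stronger readings are tempting, and the documents do not support them.

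- **That the plan fits one model with 16 covariates.** It does not say so. The 16 is a count of a data-collection column, and planning both univariate and multivariable models is equally consistent with a reduced final model. With two or three covariates and a 10-15% event rate, nearly all fits are estimable and few are extreme. What stands is that no rule keeps the model that small, and that small models also fail often at 2-5%.
- **That the trial has no comparison of arms on clinical events, or that the Cox models miss the trial's question.** Log-rank testing is planned, the hypothesis concerns platelet reactivity, and the models are labelled further analysis. The arm is absent by silence; it is not explicitly excluded. What stands is narrower: no hazard ratio with confidence interval is specified for arm.
- **That the stent model is almost certain to fail.** Non-estimability above 90% with 16 covariates belongs to event rates of 1-2%, as might be assumed for thrombosis alone. The planned outcome combines thrombosis and restenosis. At 5% the figure is about 52%, and at 10% it is 7-9%.
- **That the false-positive rate shows 132 is too few.** In simulation 58-62% of fitted 16-covariate models had at least one p below 0.05, but 1 - 0.95^16 = 56% is expected from multiplicity at any sample size.

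It is also fair to say that the univariate models can be fitted when events suffice, and that arm plus stratum is itself two terms, needing 20 events by the same benchmark. Penalisation eases that but does not add information.

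**Conclusion.** The concern holds in a limited form. The plan allows multivariable Cox models of any size for three outcomes. At assumed rates of 2-15% each outcome would have about 3-20 events. Ten events per variable cannot be met for 16 covariates at any event rate, and for two covariates only from about 15%. Large models would be unstable for MACCE and often not estimable for the rarer outcomes. Univariate screening of all listed characteristics would add about 2.4 chance findings if nothing is truly associated. No effect estimate with an interval is planned for chewed versus integral.

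The event rates and the events-per-variable benchmark are assumptions from outside the documents. The shortfall for 16 covariates at 10 per variable does not depend on the event rate; the other figures do. This is a secondary analysis, and the primary PRU comparison is not affected. The change should be made, but the trial's main conclusion does not depend on it.

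**What to change.** Amend the Statistical Analysis section as follows.

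1. Keep the log-rank test. Alongside it, report the MACCE hazard ratio for chewed versus integral from a Firth-penalised Cox model that includes the randomisation stratum (NSTE-ACS or stable CAD), with a profile-likelihood 95% confidence interval.
2. Report stent thrombosis, restenosis and repeat revascularization as counts by arm with exact confidence intervals.
3. If baseline-predictor models are kept, label them exploratory, state in advance how the observed number of events caps the number of covariates, and make no claims of significance.

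Firth penalisation is one reasonable choice among several. It suits this setting because it gives finite estimates when events are few, and it is available in the SAS 9.4 already named in the plan. The cost is SAP wording only, with no new data or visits. What is lost is a multivariable list of predictors, which these data are unlikely to support.
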